Study Design	
This is a Phase 2a, multi-center, open-label study, conducted in two cohorts of patients diagnosed with acute liver failure/severe acute liver injury (ALF/ALI) who meet inclusion/exclusion criteria. Cohort 1 is defined as patients with ALF/ALI with minimal renal dysfunction at the time of enrollment (defined as a serum creatinine ≤ 1.5 mg/dL and mean arterial pressure of >65 mm Hg). Cohort 2 is defined as patients with ALF/ALI with compromised renal function (defined as a serum creatinine >1.5 mg/dL and <10 mg/dL with mean arterial pressure of >65 mm Hg).
 
Informed consent will be obtained from the patient and/or patient's legally authorized representative (LAR) or family member as defined in 21CFR50.3(m). All patients will receive medical care for acute liver failure/severe acute liver injury according to the institution's standards of care. Standard of care may include, but is not limited to, administration of N-acetylcysteine and consideration for orthotopic liver transplantation.
 
Up to 36 evaluable patients will be enrolled. An evaluable patient is one who has received an infusion of OCR-002 for at least 72 hours. It is expected that not every enrolled patient will be treated for at least 72 hours due to transplant, death or early hospital discharge. Due to this, we anticipate 25% of the enrolled population will fail to reach evaluable status. Therefore, we plan to enroll up to 50 patients in order

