6.3.2 Enrollment

Patients will be considered enrolled into the study once informed consent has been obtained, all eligibility criteria are met, and the study drug infusion has been initiated. A study identification number will be assigned by the computer system that houses the study database. A Screen Failure Log will be maintained to capture basic information on all patients screened for the study but who failed to be enrolled. This would include demographic information and the reasons for failure to enroll.

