6.3.4 Discontinuation of Study Treatment

An Investigator may discontinue a patient's treatment at any time to protect the patient's safety. Reasons that patients may have treatment discontinued include, but are not limited to the following:

- Prolongation of Qt/Qt_c interval of >60 msec over baseline or a Qt/Qt_c interval above 500 msec;
- Evidence of torsades de pointe phenomenon;
- Grade 3 or higher CTCAE toxicity not attributed to acute liver failure in the opinion of the investigator;
- Neutropenia with absolute neutrophil count <500/cumm or platelet count <20,000/cumm, or an increase in serum Cr to a value of >10mg/dL;
- Liver transplantation during the study treatment;
- Withdrawal of informed consent by the patient or patient's legally authorized representative or family member;
- In the case of interruption of infusion for any reason, the study drug will not be restarted if more than 2 hours has elapsed;
- Evidence of shock; and
- Evidence of kidney injury related to study drug will invoke consideration of discontinuation of the study drug.

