11.4 Analysis Population

The intent-to-treat (ITT) population will include all patients who consented to the study, completed screening and were initiated intravenous infusion of study drug. The ITT population will serve as the basis for a sensitivity analysis of the PP results for all endpoints.

The per-protocol (PP) population (evaluable population) will include all patients who receive at least 72h of OCR-002 in accordance with protocol timelines. The PP population will be used for the primary analysis of all outcomes.

The safety population will include all patients who completed screening and were enrolled into the trial.

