11.6 Statistical Analyses

Tables and listings will be produced using SAS v9.2 or higher (SAS, Cary, NC). Data summaries by cohort group will be presented. For continuous variables, data will be summarized with the number of patients, mean, standard deviation, median, and minimum and maximum overall and by cohort. For categorical variables, data will be tabulated in frequency tables to display the number and proportion of patients for each category overall and by cohort. Baseline assessments for each outcome variable will be defined as the last measurement obtained before treatment initiation. Each point estimate will be presented with 2-sided 95% confidence intervals and all statistical tests will use a two-sided 5% significance level.

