11.7.2 Clinical Laboratory Tests

Clinical laboratory test parameters will be listed for individual patients. Baseline for clinical laboratory parameters will be defined as the last evaluation before the start of the initial dosing with study drug. Summary statistics, including mean absolute change from baseline, will be calculated for each parameter and summarized.

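### Section 11.4 makes patients with at least 72 h of drug the primary set for all outcomes, so the primary safety tables omit about a quarter of those treated, and the safety population has no assigned analysis

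*Combined protocol and SAP*

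**What the plan says.** Section 4.1.1 makes safety and tolerability the primary objective. Section 4.2.1 lists physical examinations, vital signs, laboratory tests, ECGs and adverse events as the safety endpoints.

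Section 11.4 defines three populations:

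- **PP (evaluable):** at least 72 h of drug, given within protocol timelines. "The PP population will be used for the primary analysis of all outcomes".
- **ITT:** consented, screened and infusion started. "The ITT population will serve as the basis for a sensitivity analysis of the PP results for all endpoints".
- **Safety:** "The safety population will include all patients who completed screening and were enrolled into the trial". Neither 11.4 nor 11.7 gives this population an analysis.

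Under section 6.3.2 a patient counts as enrolled only once consent is obtained, "all eligibility criteria are met, and the study drug infusion has been initiated". The safety and ITT populations are therefore in effect the same patients.

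The synopsis expects that "not every enrolled patient will be treated for at least 72 hours due to transplant, death or early hospital discharge". Section 6.3.4 adds reasons why drug may be stopped. They include QT prolongation, Grade 3 or higher toxicity not attributed to the liver failure, shock, and laboratory limits: "Neutropenia with absolute neutrophil count <500/cumm or platelet count <20,000/cumm, or an increase in serum Cr to a value of >10mg/dL".

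For laboratory tests, section 11.7.2 plans individual listings and this: "Summary statistics, including mean absolute change from baseline, will be calculated for each parameter and summarized". The general rule in 11.6 is: "For continuous variables, data will be summarized with the number of patients, mean, standard deviation, median, and minimum and maximum overall and by cohort". The closing memorandum confirms that section 11 is the whole statistical plan.

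**The concern.** Entry to the primary set depends partly on what the safety analysis should measure. A patient whose drug is stopped at 40 h for shock, a long QT interval or a falling platelet count has shown intolerance, and for that reason never reaches 72 h. The conflict is sharpest in section 11.7.1, which counts patients who withdraw because of an AE. In the PP set that count can include only withdrawals at or after 72 h.

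At stake is which table carries the answer to the primary objective. As written, the headline safety result describes patients who stayed on drug for three days, and the result for everyone exposed is a sensitivity analysis.

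**Working it through.** **Inputs.** Synopsis: 36 evaluable patients, 25% expected not to reach evaluable status, up to 50 enrolled. Section 3.3.2: up to 12 evaluable at Dose Level 4. Section 11.3 reports no formal sample size calculation, so the only planning figure to reproduce is the enrolment target.

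**Step 1, the plan's own figure.** 36 / (1 − 0.25) = 48. The stated ceiling of 50 is consistent with this, with two patients to spare.

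**Step 2, treated patients outside the primary set.**

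- At the stated attrition: 48 − 36 = 12, and 12/48 = 25%.
- At the ceiling with 36 evaluable: 50 − 36 = 14, and 14/50 = 28%.
- At Dose Level 4, assuming the same 25% applies: 12/0.75 = 16 treated, so 4 outside.

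**Step 3, what a zero count can rule out.** The upper end of the exact two-sided 95% interval for 0/n is 1 − 0.025^(1/n).

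| Set | n | Upper limit |
|---|---|---|
| PP | 36 | 9.7% |
| All treated, 25% attrition | 48 | 7.4% |
| All treated, ceiling | 50 | 7.1% |

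**Step 4, direction.** The documents give no event rates, so this is an illustration. Suppose 4 of 50 treated patients have a given event: 4/50 = 8.0% (exact 95% CI 2.2% to 19.2%).

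| Of the 4, stopped before 72 h | Primary (PP) result |
|---|---|
| 0 | 4/36 = 11.1% |
| 1 | 3/36 = 8.3% |
| 2 | 2/36 = 5.6% |
| 4 | 0/36 = 0% |

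The primary figure can lie above or below the all-treated figure. What is certain is narrower: an event that stops the drug before 72 h cannot appear in the PP table. A toxicity stop between 72 h and 120 h stays in it.

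**Step 5, laboratory display (supports the optional addition only).** The summaries in 11.6 include the minimum, so they show that a limit was crossed, but not by how many patients. Two constructed sets of 18 platelet counts (thousands) make the point:

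- 15, 24, 24, 31, 32, 34, 54, 60, 64, 66, 85, 88, 88, 94, 105, 106, 140, 150
- 15, 17, 18, 19, 19, 61, 64, 64, 64, 66, 92, 94, 95, 100, 100, 110, 112, 150

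Both have mean 70, SD 40.0, median 65, minimum 15 and maximum 150. The first has 1/18 (5.6%) below 20 and the second 5/18 (27.8%). The planned listings would allow a hand count.

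**The case against.** The strongest reply is that 11.4 is loosely worded and the intent is plain. A safety population has no purpose unless safety is analysed in it, a count of AE withdrawals makes little sense in patients selected for staying on drug, and the synopsis says that all adverse events will be summarized. That reading is plausible. But the sentence on PP covers all outcomes without exception, the synopsis names no population, and no later document settles it.

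The second reply is that little is lost, and much of this stands:

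- The ITT sensitivity analysis covers every endpoint in everyone treated.
- Section 9.1.2 requires disease-expected events to be recorded. Its list includes neutropenia, thrombocytopenia, azotemia and acute renal failure. Section 11.7.1 then tabulates AE incidence and severity by cohort.
- Sections 9.1.3 and 9.8 turn many laboratory abnormalities into AEs, though with some judgement on disease attribution or clinical significance.
- The Safety Review Committee sees all enrolled patients quarterly, and section 9.7 adds a review of all of them at study completion.

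A reader might infer that early toxicity goes unrecorded or unmonitored, or that dose escalation and stopping are weakened. The documents do not support either inference: these routes remain, and the escalation and stopping rules do not use the PP set. A reader might also infer that the primary tables understate toxicity throughout. That holds only for stops before 72 h, because the excluded group also contains deaths, transplants and early discharges.

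Finally, this is a small, descriptive, open-label pilot, and the dose-ranging study summarized in section 3.3.2 reported no clinically significant laboratory abnormality. That limits the seriousness of the point but does not justify making the 72 h set primary for safety.

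**Conclusion.** The point holds as a matter of which population is primary. Followed as written, the plan answers its primary objective in a set that omits 25% to 28% of treated patients, including every toxicity stop before 72 h. The size rests on the plan's own attrition figure and enrolment ceiling. The Dose Level 4 figure further assumes that attrition is the same at every dose, and the four-event illustration is hypothetical. The net direction for laboratory values in general cannot be stated.

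This should be corrected, but it is not a defect that hides data. The lack of a threshold count in 11.7.2 is a lesser matter: AE terms and listings cover part of it. Baseline-to-worst shift tables, extra creatinine cut-points and a split by dialysis are reporting preferences, and nothing in the documents makes them necessary.

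**What to change.** **Main change, section 11.4.** State that the safety population, meaning all patients who started the infusion, is primary for every safety and tolerability outcome in 11.7, with PP as a supporting analysis. Keep PP as planned for PK and exploratory efficacy. Defining the population by the start of infusion also avoids doubt about a patient treated in error, because enrolment under 6.3.2 requires eligibility as well.

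The cost is wording. No new patients, data or population are needed, and the ITT repeat of the safety tables, already planned, becomes the primary version.

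**Optional addition, section 11.7.2.** By cohort and overall, give the number of patients newly crossing each 6.3.4 limit (neutrophils <500/cumm, platelets <20,000/cumm, creatinine >10 mg/dL) among those tested and not already beyond it at baseline. The qualifier matters because eligibility sets no platelet or neutrophil floor. The protocol specifies only hematology, so differentials may be missing for some patients and the neutrophil denominator smaller.

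The downside is a few more tables and wide intervals. Assuming equal cohorts, a zero count has an upper limit of 14.2% (0/24) or 13.7% (0/25) per cohort in all treated patients, against 18.5% (0/18) in PP. Without a control arm, none of these counts attributes cause.

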5 INVESTIGATIONAL PLAN

5.1 *Study Design*

This is a Phase 2a, multi-center, open-label study, conducted in two cohorts in patients

diagnosed with acute liver failure/severe acute liver injury (ALF/ALI) who meet inclusion/exclusion criteria. The acetaminophen adduct assay will be used as an additional test for equivocal or presumed cases of acetaminophen toxicity, where the history is not substantiated and the assay for acetaminophen itself proves to be negative.

Up to 36 evaluable patients are planned to be enrolled in two cohorts:

Cohort 1 will include patients with ALF/ALI with minimal renal dysfunction at the time of enrollment (defined as serum creatinine ≤ 1.5 mg/dL and mean arterial pressure of >65 mmHg).

Cohort 2 will include patients with ALF/ALI with compromised renal function (defined as a serum creatinine >1.5 mg/dL and <10 mg/dL) and mean arterial pressure of >65 mmHg.

Informed consent will be obtained from the patient and/or patient's legally authorized representative or family member [as defined in 21CFR50.3(m)]. All patients will receive medical care for acute liver failure/severe acute liver injury according to the institution's standards of care. Standard of care may include, but is not limited to, administration of NAC and consideration for orthotopic liver transplantation. All patients in Cohort 2 with a serum Cr level of ≥ 2.0 will be considered for placement on continuous veno-venous hemodialysis (CVVHD) for an appropriate interval as standard of care for this condition.

The initial dose of OCR-002 will be initiated once consent is obtained, all eligibility criteria are confirmed to be met and all baseline measurements have been completed. The infusion may begin after obtaining signed informed consent; or, up to 32 h after obtaining consent should the time be necessary to complete any pre-study drug initiation requirements and/or to provide a time frame for study drug administration.

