8.1 Screening

Patients will be evaluated for entry into the study according to the stated inclusion and exclusion criteria. Individuals who are identified during screening as not eligible for the study need not complete all screening procedures. The reason for ineligible status will be documented on the Screen Failure Log.

The following procedures will be obtained or performed to evaluate each patient's general health and qualifications for participation in the study:

- Demographic information including gender, date of birth, race and ethnicity;
- Medical and medication history over the past 30 days, including prescription and non-prescription over-the-counter medications, herbal medications, vitamins, and minerals;
- Collection of blood for hematology, coagulation, clinical chemistry, ammonia* and in female patients, a pregnancy test**;

*** Venous sampling is the protocol-preferred method of collection for ammonia samples. Arterial ammonia samples will be accepted if this is the available method; however, this same method should be used for all subsequent ammonia samples for the patient.**

**Urine pregnancy test or blood human chorionic gonadotropin (hCG) is acceptable.

- Urinalysis***;
 - ***Urinalysis: dipstick plus microscopic evaluation of sediment, if clinically indicated.
- Physical examination, including height and weight (body mass index will be calculated based on these variable), and vital signs (systolic and diastolic blood pressure, pulse rate, respiratory rate, body temperature);
- 12-lead ECG;
- Neurological battery, including
 - Glasgow Coma Scale;
 - West-Haven Scale; and
 - O-Log Scale;
- Review inclusion and exclusion criteria; and
- Signed, written informed consent.

The start of the initial infusion may begin after obtaining signed informed consent; or, up to 32 h after obtaining consent should the time be necessary to complete any pre-study drug initiation requirements and/or to provide a time frame for study drug administration. Patients will be considered enrolled once the informed consent has been obtained, all eligibility criteria have been met, and the study drug infusion initiated.

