9.7 Safety Review Committee

The Safety Review Committee (SRC) will consist of three experienced ALFSG clinicians and a clinical pharmacologist with experience in clinical trials and PK measurement. All are independent of any clinical site participating in the trial and will exercise oversight of the safety of trial participants, review periodic safety reports prepared by the SDCC biostatistician, request additional data/information (if necessary), and advise the trial Sponsor and Executive Committee regarding continuation/discontinuation of the study. A primary responsibility of the SRC is to review the safety and PK data (as provided by the SDCC) and to provide recommendations on proceeding to the next dose level.

Throughout the trial the SRC will review all safety data at regular intervals and after each dose level in each cohort. In addition, the SRC will review safety and PK data for the evaluable Cohort 1 patients who complete Dose Levels 1 and 2 to determine if it is safe to enroll Cohort 1 patients into Dose Level 3 and Cohort 2 patients into Dose Level 1. Another review will be conducted prior to enrolling Cohort 2 patients into Dose Level 3. During these two specific reviews, enrollment will be paused. The SRC will also review the safety and PK data for the evaluable Cohort 2 patients who complete Dose Level 3 to determine if it is safe to enroll Cohort 2 patients into Dose Level 4. Upon completion of the study, the SRC will review safety data for all enrolled patients.

In addition to the SRC review, the IMM in consultation with the external MSM will closely monitor the incidence rates of all adverse events reported and will alert the SRC if a trend is observed for AEs collected from Baseline through the 24 hours Following the Completion of the Last Infusion period and for SAEs collected from Baseline through the Day 30 post treatment period. A summary of all AEs and SAEs, a summary of all expedited safety reports, and a listing of all patients who were terminated from the study due to study-related adverse events, will be included in reports submitted by the SDCC to the Executive Committee, the MSM, and the SRC. An annual report will be submitted to the FDA.

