11.5 Interim Analysis

There are no interim analyses planned as this is an open-label study; however, safety data will be reviewed by the SRC continuously throughout the study period. In addition to specific dose level reports, quarterly safety reports on all enrolled patients will be provided to the SRC during the study period. These reports will include summary tables overall and by cohort and site on baseline characteristics, treatment completions and reasons for early treatment withdrawals, study completions rates and all outcomes related to safety information including all adverse events and serious adverse events.

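### The safety population is tied to enrolment, and so to eligibility, rather than to exposure; a dosed patient with an unmet criterion could fall outside it

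*Combined protocol and SAP*

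**What the plan says.** Section 11.4 defines three analysis sets.

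- **Safety population:** "The safety population will include all patients who completed screening and were enrolled into the trial."
- **ITT:** "all patients who consented to the study, completed screening and were initiated intravenous infusion of study drug". It is the sensitivity analysis for every endpoint.
- **Per-protocol (PP):** patients with at least 72 hours of OCR-002. "The PP population will be used for the primary analysis of all outcomes."

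Enrolment is defined twice. In section 6.3.2 patients are "considered enrolled into the study once informed consent has been obtained, all eligibility criteria are met, and the study drug infusion has been initiated". Section 8.1 repeats it: "Patients will be considered enrolled once the informed consent has been obtained, all eligibility criteria have been met, and the study drug infusion initiated."

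Two SRC provisions use the same word. Section 11.5 says that "quarterly safety reports on all enrolled patients will be provided to the SRC", and section 9.7 says that at study completion "the SRC will review safety data for all enrolled patients".

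The memorandum at the end of the document confirms that no separate SAP was written, so section 11.4 is the only place where the sets are defined.

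**The concern.** The primary objective is safety and tolerability, and a safety set should hold everyone exposed to the drug. Here membership runs through enrolment, and enrolment runs through eligibility. If eligibility is taken as finally established, a patient who was dosed and later found to have an unmet criterion is not enrolled in the defined sense and so is not in the safety population. Such patients may have a different disease or a different risk, and their adverse events would leave the safety denominator and numerator together. The safety set could then be narrower than the ITT set, which is the reverse of the usual order.

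**Working it through.** **1. The definitions side by side.**

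| Status or set | Consent | Screening completed | All criteria met | Infusion started |
|---|---|---|---|---|
| Enrolled (6.3.2, 8.1) | required | not named | required | required |
| Safety (11.4) | through enrolment | required | through enrolment | through enrolment |
| ITT (11.4) | required | required | not named | required |

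On a literal reading the safety set carries every ITT condition plus eligibility. It can equal the ITT set or be smaller, but never larger.

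**2. Two test patients, both consented and dosed.**

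- Patient A completed screening but had an unmet criterion: not enrolled, so outside the safety set; inside ITT.
- Patient B lacked a screening procedure: outside the safety set and outside ITT.

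Only patient A makes the safety set smaller than ITT. Patient B is exposed but in neither set.

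**3. Can patient A arise?** Section 5.1 says "The initial dose of OCR-002 will be initiated once consent is obtained, all eligibility criteria are confirmed to be met", and section 7.4 sets the same condition, so the plan does not intend it. Some criteria may nevertheless not be final by then. Dosing can start straight after consent and at most 32 hours later (5.1, 7.4). In section 6.2.1 an indeterminate cause requires other viruses to be ruled out, and the HSV and CMV definitions refer to a fourfold rise between acute and convalescent sera; the second sample comes later. Drug-induced injury requires other causes to be excluded, and autoimmune hepatitis may rest on biopsy. Section 5.1 sends equivocal acetaminophen cases to an adduct assay. A revised etiology after dosing is therefore possible. The documents do not say how often.

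**4. What the SRC sees.**

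| SRC input | Scope | Tied to enrolment? |
|---|---|---|
| Ongoing and dose-level reviews (9.7) | all safety data | no |
| Report under the stopping criteria (9.7.1) | every reported AE and SAE, with individual listings | no |
| Quarterly reports (11.5) | enrolled patients | yes |
| End-of-study review (9.7) | enrolled patients | yes |

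**5. Size.** The plan's enrolment figure comes first, because it supplies the denominator. The synopsis gives 36 evaluable patients with 25% expected not to become evaluable: 36 / (1 − 0.25) = 48, consistent with the stated maximum of 50.

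Illustration with one affected patient who has the only event of its kind among 50 dosed (exact two-sided 95% intervals):

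- By exposure: 1/50 = 2.0%. Lower limit 1 − 0.975^(1/50) = 0.05%; upper limit 10.6%, the value of p at which P(X ≤ 1) = 0.025 with n = 50.
- By the literal definition: 0/49 = 0%. Upper limit 1 − 0.025^(1/49) = 7.3%.

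The rate of dosed but ineligible patients has to be assumed. With p = 2%, 5% or 10%, independent between patients, the expected number among 50 is 50p = 1, 2.5 or 5, and the chance of at least one is 1 − (1 − p)^50 = 64%, 92% or 99%. These are chances that such a patient exists, not that the patient is left out or has an event.

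**The case against.** The strongest reply is that nothing in the protocol removes a dosed patient from any set. Enrolment is a status reached when the infusion starts, after eligibility has been confirmed, and a later change of diagnosis need not undo it. Section 6.3.5 follows patients who stop drug through the 30-day study period unless consent is withdrawn, and section 6.3.3 keeps data collected before withdrawal of consent. Adverse events are recorded from the first administration (section 9). The ITT sensitivity analysis would keep patient A, and the AE tabulations in section 11.7.1 name no population at all. All of this stands. It means that exclusion is one reading of the text and not a stated rule. It does not settle which reading applies, and with no SAP nothing else does.

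A reader might infer two stronger things. The first is that ineligible dosed patients are in fact dropped; no section says so. The second is that the SRC would miss them when it decides on escalation. The documents point the other way: dose-level reviews cover all safety data, the external medical safety monitor reviews every SAE entered (9.5), and the stopping rules count patients within a dose level, not members of the safety population. Carrying the assumed rates down to a three-patient dose group would therefore say nothing about escalation.

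It can also be said that the choice of PP as primary for all outcomes matters more to safety reporting, since the plan itself expects 25% of patients not to reach evaluable status. That is a separate issue. It bears here only because redefining the safety set changes no table unless the safety tables are assigned to it.

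**Conclusion.** The point holds as a defect of definition. The safety population is not defined by exposure and, read literally, could leave out a dosed patient whom the ITT set keeps. Within SRC oversight the same wording reaches only the quarterly reports and the end-of-study review. The conclusion rests on reading eligibility as finally established; if it means eligibility as confirmed at infusion start, patient A stays in, though patient B is still left out by the screening condition. The size is unknown because no ineligibility rate is given, so the 1/50 against 0/49 contrast shows only what a single patient can do. The change is worth making because safety is the primary objective and the correction costs almost nothing.

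**What to change.** - In section 11.4, replace the definition with: *Safety population: every patient in whom an OCR-002 infusion was started, whether or not the eligibility criteria were met or screening was complete.*
- In section 11.7, state that the safety tables and listings use this population.
- In sections 9.7 (end-of-study review) and 11.5 (quarterly reports), replace the reference to enrolled patients with *all patients who received any OCR-002*.
- Flag eligibility deviations in the listings, so that these patients can be identified and not removed.

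The cost is wording only. Possibly a few more patients appear in the safety tables, and no dose or clinical rule changes.
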